10.5.2 Analyses of Other Secondary Efficacy and Selected Exploratory Endpoints

The analysis of the following secondary and exploratory endpoints at week 24 will be performed using the LDI analysis set for LDI endpoints, SPARCC Enthesitis analysis set for SPARCC endpoints, mNAPSI analysis set for mNAPSI endpoints, and the full analysis set for the other efficacy endpoints unless otherwise specified:

- LDI change from baseline at week 24 (LDI analysis set)
- Achievement of LDI=0 at week 24 (LDI analysis set).
- SPARCC change from baseline at week 24 (SPARCC analysis set)
- Achievement of SPARCC=0 at week 24 (SPARCC analysis set)
- mNAPSI change from baseline at week 24 (mNAPSI analysis set)
- Achievement of mNAPSI=0 at week 24 (mNAPSI analysis set)
- PASDAS change from baseline at week 24
- DAS28-CRP change from baseline at week 24
- SDAI change from baseline at week 24
- CDAI change from baseline at week 24
- VLDA at week 24
- DAPSA change from baseline at week 24

For binary endpoints, treatment effect will be tested using the stratified CMH test with BMI and prior non-biologic DMARD use as the stratification factors. For continuous endpoints that exhibit normal distribution, ANCOVA model will be used. The model will include treatment groups and baseline BMI and prior non-biologic DMARD as covariates. For continuous endpoints that are not normally distributed, endpoint data will be first transformed to their joint ranks and then further transformed by the Van der Waerden transformation to normalize them before applying the ANCOVA model. The significance level for other secondary endpoints will be 0.05 without adjusting for multiplicity and p-values will therefore be treated as a descriptive statistic only. All the testing will be performed for endpoints at week 24 and methotrexate monotherapy group will be the reference group.

Analyses to other secondary endpoints will be summarized descriptively only. sPGA and BSA summary analyses will be performed using psoriasis efficacy analysis set and subgroups of subjects with the baseline BSA < 3%, > = 3% but < 10%, and > = 10%.

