This study will also aim to characterize the response rates of etanercept on enthesitis, dactylitis, and psoriatic nail changes. The PRESTA trial, assessed two different regimens of etanercept (50 mg twice weekly or 50 mg once weekly) in subjects with psoriasis and PsA. Etanercept 50 mg once weekly resulted in a 70.0% and 81.3% improvement from baseline in enthesitis at week 12 and 24 respectively. Similarly, improvement in dactylitis from baseline at weeks 12 and 24 were 78.4% and 84.8%, respectively (Sterry et al, 2010). There is a paucity of data regarding the efficacy of methotrexate monotherapy on dactylitis and enthesitis in patients with PsA. A recent study looking at the effect of etanercept on the Nail Psoriasis Severity Index (NAPSI) score at week 12 and 24 improved by 50% and 72%, respectively on a weekly dose of Enbrel of 50 mgs (Ortonne et al, 2013). In another recent study comparing improvement in nail changes on methotrexate monotherapy compared to cyclosporine monotherapy, methotrexate demonstrated a 30% improvement at 12 weeks and a 54% improvement at 24 weeks in the NAPSI score (Gümüşel et al, 2011).

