## **10.5 Planned Methods of Analysis**

### **10.5.1 General Considerations**

Subject disposition, demographics, and baseline disease characteristics will be summarized descriptively by randomized treatment group.

For categorical endpoints, the descriptive statistics will contain the frequency and percentage. For continuous endpoints, the descriptive statistics will include the number of observations, mean, standard error, standard deviation, median, minimum, and maximum.

Treatment effect will be tested for the primary and key secondary endpoints using a Bonferroni-based gatekeeping chain procedure to control the family-wise 2-sided type one error rate at 0.05. The significance level for the analyses of other secondary endpoints and exploratory endpoints will be 0.05 without adjusting for multiplicity and the p-values for these endpoints will therefore be treated as a descriptive statistic only.

Safety endpoints will be tabulated by actual treatment received during the study. No formal statistical testing will be performed for safety analyses.

Details of all statistical methods will be provided in the SAP.

[figure not shown]

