### **10.5.3 Other Secondary Efficacy Endpoints**

The primary analysis of other secondary endpoints will be performed using the full analysis set for non-psoriasis endpoints or the psoriasis efficacy analysis set for psoriasis endpoints. For binary endpoints, treatment effect will be tested using the stratified CMH test with BMI and prior non-biologic DMARD use as the stratification factors. For continuous endpoints that exhibit normal distribution, ANCOVA model will be used. The model will include treatment groups and baseline BMI and prior non-biologic DMARD as covariates. For continuous endpoints that are not normally distributed, endpoint data will be first transformed to their joint ranks and then further transformed by the Van der Waerden transformation to normalize them before applying ANCOVA model. The significance level for other secondary endpoints will be 0.05 without adjusting for multiplicity and p-values will therefore be treated as a descriptive statistic only.

Data will be analyzed as observed with no imputation for missing data.

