## **12. ADMINISTRATIVE AND LEGAL OBLIGATIONS**

### **12.1 Protocol Amendments and Study Termination**

If Amgen amends the protocol, agreement from the Investigator must be obtained. The IRB/IEC must be informed of all amendments and give approval. The investigator must send a copy of the approval letter from the IRB/IEC to Amgen.

Amgen reserves the right to terminate the study at any time. Both Amgen and the Investigator reserve the right to terminate the Investigator's participation in the study according to the study contract. The investigator is to notify the IRB/IEC in writing of the study's completion or early termination and send a copy of the notification to Amgen. Subjects may be eligible for continued treatment with Amgen investigational product(s) by an extension protocol or as provided for by the local country's regulatory mechanism. However, Amgen reserves the unilateral right, at its sole discretion, to determine whether to supply Amgen investigational product(s) and by what mechanism, after termination of the study and before the product(s) is/are available commercially.

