In a recent randomized placebo-controlled trial of methotrexate monotherapy in PsA ([Kingsley et al, 2012](#)) the ACR 20 response rate for the methotrexate monotherapy arm was 34%. However, the dose of methotrexate was 15 mg QW. Assuming a higher dose of methotrexate (ie, 20 mg QW) would yield better responses, the response rate for the methotrexate monotherapy arm in this planned phase 3 study is assumed to be 44%.

Therefore, in order to detect a difference of 16% between the etanercept monotherapy and methotrexate monotherapy arms, using a two-sided Chi-square test at a significance level of 0.025 and 90% marginal power, each treatment arm will have approximately 280 subjects adjusting for an anticipated 10% dropout.

This sample size will provide marginal power > 90% to detect a treatment difference in ACR 20 response at week 24 between the etanercept plus methotrexate therapy arm and the methotrexate monotherapy arm at a two-sided 0.025 significance level. As previously mentioned, the ACR response rate at week 24 is assumed to be 44% for the methotrexate monotherapy arm. The ACR response rate at week 24 for the etanercept plus methotrexate therapy arm is assumed to be 5% higher than the etanercept monotherapy arm (ie, 65%). This is based on a longitudinal observational study assessing the role of TNF-inhibitor plus methotrexate combination therapy versus TNF-inhibitor monotherapy ([Fagerli et al, 2014](#)).

In addition, this sample size will provide marginal power > 90% to detect treatment differences in MDA response at week 24 between both etanercept arms and the methotrexate arm at a two-sided 0.025 significance level, assuming response rates of 15%, 30%, and 35% for the methotrexate monotherapy, etanercept monotherapy, and etanercept plus methotrexate therapy arms, respectively. In recent PsA trials, the MDA 24-week response rates for the placebo arm range from 3 to 7% (Coates et al, 2010a; Kavanaugh et al, 2013). Therefore, for the methotrexate monotherapy arm, the response rate is assumed to be higher at 15%. In the pivotal phase 3 randomized placebo-controlled trial of etanercept in PsA, the MDA response rate for the etanercept monotherapy arm is estimated to be approximately 20% at week 24 (data on file). For a methotrexate naïve population, the response rate is assumed to be higher at 30%. In addition, the etanercept plus methotrexate therapy arm is assumed to have a 5% improvement over the etanercept monotherapy arm.

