9.6 Distributional Characteristics

All continuous endpoints that will be analyzed with an ANCOVA model will be evaluated with regards to their distributional characteristics. If they deviate from normality, data will be first transformed to their joint ranks and then further transformed by the van der Waerden method to normalize them before applying the ANCOVA model.

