10.6.5 Exposure to Concomitant Medication

A summary of all concomitant medications reported may be provided by preferred term as coded by the World Health Organization Drug (WHODRUG) dictionary.

11. Changes From Protocol-specified Analyses

Changes are made only for secondary or exploratory endpoints. The changes are instituted to adopt the standardized ways to report the efficacy endpoints in PsA trials.

The changes to LDI, SPARCC, and mNAPSI are made to focus on relevant sub-populations for analysis. Modeling analyses described in [Section 10.5.2](#) will be

limited to selected secondary endpoints at week 24 only, for the inclusion in CSR.
Further analyses may be performed later on an ad hoc basis.

Specifically, the changes are as follows:

1. These analysis sets are added to the SAP because they are more relevant to the purpose of the analyses focusing on the subpopulations with disease progression.

Leeds Dactylitis Index (LDI) Analysis Set

The leeds dactylitis index analysis set will consist of all the randomized subjects with non-zero LDI at baseline. Subjects will be analyzed according to their randomized treatment group. Analyses of LDI efficacy endpoints will be based on the leeds dactylitis index analysis set.

Modified Nail Psoriasis Severity Index (mNAPSI) Analysis Set

The mNAPSI analysis set will consist of all the randomized subjects with non-zero mNAPSI at baseline. Subjects will be analyzed according to their randomized treatment group. Analyses of mNAPSI efficacy endpoints will be based on this analysis set.

SPARCC Enthesitis Analysis Set

The SPARCC Enthesitis Analysis Set will consist of the randomized subjects with non-zero SPARCC enthesitis at baseline. Subjects will be analyzed according to their randomized treatment group. Analyses of SPARCC efficacy endpoints will be based on the SPARCC Enthesitis analysis set.

2. Modification of the other secondary endpoints limited to specific subpopulation in in [Section 4.1.3](#) as follows:

For subjects with non-zero mNAPSI at baseline,

- mNAPSI and change from baseline at week 24
- achievement of mNAPSI = 0 at week 24

For subjects with non-zero Leeds Dactylitis Index (LDI) at baseline,

- LDI and change from baseline at week 24
- achievement of LDI = 0 at week 24

For subjects with non-zero Spondyloarthritis Research Consortium of Canada (SPARCC) enthesitis at baseline,

- SPARCC enthesitis score and change from baseline at week 24
- achievement of SPARCC score = 0 at week 24

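### The ANCOVA written for eight week-24 change scores leaves out each endpoint's own baseline value, which costs precision if the true baseline slope is below 1

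*SAP*

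**What the plan says.** SAP 10.5.2 lists twelve week-24 endpoints for modelling. Four are binary. The other eight are changes from baseline: LDI, SPARCC, mNAPSI, PASDAS, DAS28-CRP, SDAI, CDAI and DAPSA (DAPSA is exploratory under SAP 4.1.5). For the continuous endpoints the section states: "The model will include treatment groups and baseline BMI and prior non-biologic DMARD as covariates". Protocol 10.5.3 has the same sentence.

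Non-normal endpoints take a rank route into the same model. SAP 9.6 says: "If they deviate from normality, data will be first transformed to their joint ranks and then further transformed by the van der Waerden method". No baseline term enters there either.

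The p-values are tested at an unadjusted 0.05 level and labelled descriptive. Protocol 10.5.3 adds, on missing data: "Data will be analyzed as observed with no imputation for missing data". SAP Section 11 explains that the modelling is "limited to selected secondary endpoints at week 24 only, for the inclusion in CSR". HAQ-DI and SF-36 changes are not on the modelled list and are only summarised, so they fall outside this point.

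**The concern.** A change score subtracts the baseline value with a coefficient of exactly 1. If baseline is not also in the model, that coefficient cannot be estimated. When the regression of the week-24 value on baseline has a slope below 1, part of the baseline variation stays in the error term. The treatment estimate then also carries chance baseline differences between arms that a fitted slope would remove.

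On the untransformed route the estimate remains unbiased over randomisation, and type I error is unaffected. What is at stake is efficiency: wider standard errors than necessary for the modelled comparisons chosen for the study report. They include dactylitis, enthesitis and nail disease, which Protocol 2.4 says the study aims to characterise.

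**Working it through.** **1. Reading of the model.** SAP 4.2 defines baseline BMI as body mass index, cut at 30, and SAP 10.5.1 uses BMI and prior DMARD use as the CMH strata. The phrase therefore cannot mean the baseline score plus BMI. SAP 4.2, 9.6, 10.5.2, 10.5.3 and 11 add no own-baseline term. Appendix B is blacked out and settles nothing either way.

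**2. The plan's own figure.** The documents give no power, SD or correlation for these eight endpoints. The only planning figure needed is in SAP 3.2: "each treatment arm will have approximately 280 subjects adjusting for an anticipated 10% dropout". For 60% against 44% at two-sided 0.025 and 90% power, the formula gives 240 per arm (267 after dividing by 0.9), or 253 with continuity correction (282 after dividing by 0.9). The second agrees with 280. Evaluable subjects per arm: 280 × 0.9 = 252.

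**3. Untransformed route.** Assumptions: baseline SD = 1, week-24 SD = k, correlation ρ, and no association of the endpoint with BMI or DMARD use. The true slope is ρk.

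- Without baseline: Var(change) = 1 + k² − 2ρk
- With baseline: residual variance = k²(1 − ρ²)
- Proportional cut = (1 − ρk)² / (1 + k² − 2ρk)

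Example, k = 1 and ρ = 0.5: 0.25 / 1.00 = 25%.

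| k | ρ = 0.3 | ρ = 0.5 | ρ = 0.7 |
|---|---|---|---|
| 0.6 | 67% | 64% | 65% |
| 0.8 | 50% | 43% | 37% |
| 1.0 | 35% | 25% | 15% |
| 1.2 | 24% | 13% | 3% |

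The standard error falls by 1 − √(1 − cut): at most 42.8% (k = 0.6, ρ = 0.3) and at least 1.7% (k = 1.2, ρ = 0.7) on this grid.

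**4. What that means at k = 1.** The variance ratio, written model over adjusted model, is 2/(1 + ρ): 1.54, 1.33 and 1.18 at ρ = 0.3, 0.5 and 0.7. The written model's standard error is larger by 24%, 15% and 8%. The 252 subjects per arm act like 252(1 + ρ)/2 = 164, 189 and 214. An effect with 80% power under baseline adjustment (two-sided 0.05) has 62%, 68% and 73% as written.

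**5. The same cost seen in one trial.** One standard error of the baseline difference is √(2/252) = 0.0891 baseline SD. An imbalance of that size shifts the written estimate by (1 − ρk) × 0.0891. At k = 1 this is 0.062, 0.045 and 0.027; over the grid it runs from 0.073 to 0.014. This applies to the five full-analysis-set endpoints. Missing composite components would lower n and enlarge it. The sizes of the LDI, SPARCC and mNAPSI sets are not given.

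**6. Rank route, by simulation.** Three arms of 252; baseline exp(0.8·z0) and week-24 k·exp(0.8·z1) with corr(z0, z1) = ρ; no treatment effect; two independent binary covariates; change and baseline each given joint ranks and normal scores; 4,000 runs per cell. Mean cut in residual variance:

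| k | ρ = 0.3 | ρ = 0.5 | ρ = 0.7 |
|---|---|---|---|
| 0.6 | 49.1% | 44.1% | 41.6% |
| 0.8 | 37.8% | 30.2% | 23.8% |
| 1.0 | 29.4% | 20.5% | 12.1% |
| 1.2 | 23.0% | 13.5% | 5.1% |

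Type I error was 0.044–0.053 without baseline and 0.042–0.057 with it (Monte Carlo SE about 0.0034). With half of the week-24 scores set to zero (2,000 runs per cell), the cut was 18.9% to 57.0%.

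**7. Is a slope below 1 plausible?** Protocol 2.4 reports, for weekly etanercept in other studies, that "improvement in dactylitis from baseline at weeks 12 and 24 were 78.4% and 84.8%, respectively". It also gives week-24 improvements of 81.3% for enthesitis and 72% for nails, and 54% for nails on methotrexate. If change is proportional to baseline, the slopes are 1 − 0.848 = 0.15, 1 − 0.813 = 0.19, 1 − 0.72 = 0.28 and 1 − 0.54 = 0.46. There is also a structural reason. The LDI, SPARCC and mNAPSI sets require a non-zero baseline (SAP 7.5 to 7.7), and for any subject who reaches zero the change equals minus the baseline value.

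**The case against.** The strongest case is that nothing here is invalid. The comparison is pre-specified, its type I error holds, its p-values are descriptive, none of the eight endpoints was powered, and the covariates match the CMH strata. All of that stands, and it limits the weight of the point. It is not a reason to keep a less precise model when the better one uses data already collected.

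Four narrower objections:

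- **The gain may be nil.** Correct. It is exactly zero at slope 1 (for example ρ = 0.8, k = 1.25), and at k = 1.2, ρ = 0.8 it is 0.04²/0.52 = 0.3%. Strictly, precision is lost whenever the slope differs from 1, in either direction. If the slope is 1, the added term costs one degree of freedom.
- **The imbalance shift is not a second harm.** Correct. The excess variance of the treatment difference is (2/n)(1 − ρk)², and the shift in step 5 is its square root. It is the mechanism of the precision loss and should not be counted again.
- **The outside percentages do not identify a slope.** Correct without the proportionality assumption, and those indices and populations may differ. They are an indication only; no figure in steps 3 to 6 depends on them.
- **The fixed-slope argument belongs to the untransformed scale.** Largely so: the 67% figure does not describe an endpoint that is ranked. The simulation covers that route and still shows a gain, of 5% to 49%.

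The blacked-out code might already contain a baseline term. In that case the edit would only bring the text into line with it.

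**Conclusion.** The concern holds for the model as written. The ANCOVA for the eight week-24 change scores has no own-baseline term, and it gives up precision if the true slope is below 1. The loss may be large or trivial: on the assumed grid, adding baseline cuts residual variance by 67% to 3% untransformed and by 49% to 5% on the rank route, and the gain is nil at slope 1. These ranges rest on assumed correlations and SD ratios and on no link between the endpoint and BMI or DMARD use. The primary and key secondary conclusions are not affected. This is an efficiency gain that should be taken, not a validity defect.

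**What to change.** In SAP 10.5.2, specify the terms as treatment group, the endpoint's own baseline value, baseline BMI and prior non-biologic DMARD use. Add one sentence for the rank route: when an endpoint is van der Waerden transformed, its baseline value is ranked jointly over the subjects analysed for that endpoint and transformed in the same way. Record both in SAP Section 11 as a change from Protocol 10.5.3, before unblinding.

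The cost is one model term, one sentence and one Section 11 entry. SAP 6.2 already defines the baseline value. SAP 9.3.1 does not impute missing baselines, so a subject without one already has no change score and nobody further is lost. A protocol amendment is not needed, because Protocol 10.5.1 says "Details of all statistical methods will be provided in the SAP". Keeping the edit in the SAP also avoids the step in Protocol 12.1: "The IRB/IEC must be informed of all amendments and give approval".

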##### 10.1.1.3 Other Secondary Endpoints

- Modified NAPSI score and change from baseline at week 24
- Leeds dactylitis score and change from baseline at week 24
- SPARCC enthesitis score and change from baseline at week 24
- ACR 20 response at all other measured timepoints
- MDA response at all other measured timepoints
- Psoriatic Arthritis Disease Activity Score (PASDAS) at all measured timepoints
- ACR 50, ACR 70, and components of ACR at all measured timepoints

- Simplified Disease Activity Index (SDAI) and change from baseline at all measured timepoints
- Clinical Disease Activity Index (CDAI) and change from baseline at all measured timepoints
- Disease activity score (28 joint) using the C-reactive protein formula (DAS28-CRP) and change from baseline at all measured timepoints
- HAQ-DI score and change from baseline at week 24
- SF-36 score and change from baseline at week 24

For subjects with involved BSA  $\geq 3\%$  at baseline:

- sPGA at week 24
- BSA at week 24

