2.3 Other Secondary Objectives

To evaluate the efficacy of etanercept plus methotrexate therapy and etanercept monotherapy compared to methotrexate monotherapy on the following:

- Other measures of arthritis activity
- Measures of non-arthritic PsA disease activity
- Key patient reported outcomes (PRO) related to physical function and quality of life

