4.1.3 Other Secondary Endpoints

- ACR 20 response at all measured time points other than week 24
- MDA response at all measured time points other than week 24
- Psoriatic Arthritis Disease Activity Score (PASDAS) at all measured time points and change from baseline at all measured time points
- ACR 50, ACR 70, and components of ACR at all measured time points
- Simplified Disease Activity Index (SDAI) and change from baseline at all measured time points
- Clinical Disease Activity Index (CDAI) and change from baseline at all measured time points
- Disease activity score (28 joint) using the C-reactive protein formula (DAS28-CRP) and change from baseline at all measured time points
- Health Assessment Questionnaire Disability Index (HAQ-DI) score and change from baseline at week 24
- Short Form (36) Health Survey Version 2 (SF-36v2) (MCS and PCS) score and change from baseline at week 24

For subjects with non-zero mNAPSI at baseline,

- mNAPSI and change from baseline at week 24
- achievement of mNAPSI = 0 at week 24

For subjects with non-zero Leeds Dactylitis Index (LDI) at baseline,

- LDI and change from baseline at week 24
- achievement of LDI = 0 at week 24

For subjects with non-zero Spondyloarthritis Research Consortium of Canada (SPARCC) enthesitis at baseline,

- SPARCC enthesitis score and change from baseline at week 24
- achievement of SPARCC score = 0 at week 24

For subjects with involved body surface area (BSA) $\geq 3\%$ at baseline, $< 3\%$ at baseline, and $\geq 3\%$ but $< 10\%$ at baseline, $\geq 10\%$ at baseline:

- Static Physician Global Assessment (sPGA) categorical summary by 0,1,2,3,4,5 at week 24
- sPGA continuous summary at week 24
- sPGA of 0 or 1 (yes/no) at week 24
- sPGA one grade improvement from baseline at week 24
- sPGA two grade improvement from baseline at week 24
- BSA, change and percent improvement from baseline at week 24

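### SAP 10.5.2 leaves HAQ-DI, SF-36v2, ACR 50 and ACR 70 without a planned between-arm comparison, and the reasons in SAP Section 11 do not explain why

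*SAP*

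**What the plan says.** **Objective.** Protocol 1.3 and SAP 2.3 both set out to compare each etanercept arm with methotrexate on, among other things, "Key patient reported outcomes (PRO) related to physical function and quality of life".

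**Endpoints.** Protocol 10.1.1.3 lists "HAQ-DI score and change from baseline at week 24", "SF-36 score and change from baseline at week 24" and "ACR 50, ACR 70, and components of ACR at all measured timepoints" as other secondary endpoints. SAP 4.1.3 keeps them at that level (for example "Health Assessment Questionnaire Disability Index (HAQ-DI) score and change from baseline at week 24") and specifies SF-36v2 as the PCS and MCS scores.

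**Protocol method.** Protocol 10.5.3 applies the stratified CMH test to binary other secondary endpoints. For the remainder it says: "For continuous endpoints that exhibit normal distribution, ANCOVA model will be used". Non-normal data go through van der Waerden scores first. No other secondary endpoint is excluded. The level is a nominal 0.05, and p-values are descriptive.

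**SAP method.** SAP 10.5.2 keeps the same methods but lists 12 week-24 endpoints to which they apply. The others are covered by one sentence: "Analyses to other secondary endpoints will be summarized descriptively only".

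**Disclosure.** SAP Section 11 says that modelling is confined to selected endpoints at week 24 for the study report, and adds: "Further analyses may be performed later on an ad hoc basis".

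**The concern.** The SAP keeps a comparative objective and the endpoints that serve it, then drops the comparison. It also adds formal comparisons for VLDA and DAPSA, which are exploratory in SAP 4.1.5 and absent from the protocol's endpoint lists. Protocol-listed secondary measures of function, quality of life and higher-threshold ACR response thus rank below exploratory indices in the analysis.

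At stake is how these results can be reported. The study report would give each arm's mean or percentage but no planned treatment effect with its uncertainty. Any comparison would depend on an optional later decision about which endpoints to analyse, although the protocol had already settled that question.

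**Working it through.** **1. Contents of the SAP 10.5.2 list.** LDI (2), SPARCC (2), mNAPSI (2), PASDAS, DAS28-CRP, SDAI, CDAI, VLDA and DAPSA: 2 + 2 + 2 + 6 = 12 endpoints. With two comparisons against methotrexate each, that is 24 comparisons. None is HAQ-DI, SF-36v2, ACR 50 or ACR 70.

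**2. The documents side by side.**

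| Week-24 endpoint | Protocol status | Protocol 10.5.3 method | SAP status | SAP method |
|---|---|---|---|---|
| HAQ-DI change | Other secondary | ANCOVA | Other secondary | Per-arm summary |
| SF-36 change (PCS and MCS in SAP) | Other secondary | ANCOVA | Other secondary | Per-arm summary |
| ACR 50, ACR 70 | Other secondary | Stratified CMH | Other secondary | Per-arm summary |
| ACR components | Other secondary | By endpoint type | Other secondary | Per-arm summary |
| sPGA, BSA | Other secondary (baseline BSA ≥ 3%) | By endpoint type | Other secondary | Per-arm summary |
| VLDA | Not listed | None | Exploratory | Stratified CMH |
| DAPSA change | Not listed | None | Exploratory | ANCOVA |

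**3. What a descriptive summary contains.** SAP 10.1 defines it as frequency and percentage, or n, mean, standard error, standard deviation, median and range. It names no between-arm difference, interval or test. SAP 10.1 also sets a nominal 0.05 level for other secondary endpoints in general, but that does not restore the missing tests: 10.5.2 and Section 11 are specific and restrict them.

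**4. Do the Section 11 reasons fit?** Three are given.
- *Standardised reporting in PsA trials.* This is general and says nothing about HAQ-DI, SF-36v2, ACR 50 or ACR 70.
- *Relevant subpopulations.* This concerns LDI, SPARCC and mNAPSI.
- *Week 24 as the time point of main interest.* Week 24 is the secondary time point for HAQ-DI and SF-36v2, and is among those for ACR 50 and ACR 70. This reason supports keeping the comparison.

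**5. Is precision an obstacle?** The plan's sample size comes first. For 60% versus 44% with two-sided alpha 0.025 and 90% power:

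n = [2.241·√(2·0.52·0.48) + 1.282·√(0.60·0.40 + 0.44·0.56)]² / 0.16² = 240 per arm, or 253 with continuity correction.

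Dividing by 0.9 for dropout gives 267 and 282. The stated 280 is reproduced with the correction. At 10% dropout, 280 × 0.9 = 252 per arm are evaluable.

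At two-sided 0.05, the standardised difference detectable with 80% power is (1.960 + 0.842)·√(2/n). This is 0.250 for n = 252 and 0.237 for n = 280.

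The 95% half-width for a mean difference is 1.960·√(2/n), which is 0.175 SD and 0.166 SD respectively. For a response-rate difference it is at most 1.960·√(0.5/n), which is 8.7 and 8.3 percentage points.

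The documents give no ACR 50 or ACR 70 rates. Assuming a methotrexate rate between 10% and 30% and a 15-point difference, power with 252 per arm runs from 99% down to 94%. The trial is large enough for these comparisons to be informative.

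**6. After the change.** Adding HAQ-DI, PCS, MCS, ACR 50 and ACR 70 gives 12 + 5 = 17 endpoints and 17 × 2 = 34 comparisons, all outside the gatekeeping chain.

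**The case against.** The best defence is that this is an open reporting choice among endpoints that never carried confirmatory weight. Section 11 declares it and lists the retained endpoints. The p-values were descriptive under the protocol as well. The objective asks for an evaluation against methotrexate, not specifically a test. Per-arm means, standard errors and percentages remain, and an unadjusted difference and interval can be worked out from them. Much of this stands, and it rules out several stronger readings that a reader might infer.

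- *That these endpoints have no between-arm information at all.* They keep per-arm summaries. What is missing is a planned estimate adjusted for BMI and prior DMARD use, with its interval and test.
- *That the change is concealed.* It is disclosed. The gap is the lack of a reason that applies to these endpoints.
- *That HAQ-DI and SF-36 are the only secondary patient-reported outcomes.* Patient global assessment and joint pain are also secondary, as ACR components. HAQ-DI and SF-36 are the ones that match the objective's wording on function and quality of life.
- *That exactly 10 comparisons are lost.* Ten is what the five endpoints proposed here would add. Other endpoints and visits also lose their planned tests, and the PCS/MCS split comes from the SAP, not from the protocol endpoint list.
- *That any later comparison is necessarily post hoc.* Protocol 10.5.3 remains on record, and an analysis that followed it could be traced to it. The SAP makes no commitment to run one.

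Patient-reported items also enter composites that are tested: ACR 20, MDA, VLDA, DAPSA and PASDAS, which uses SF-36 PCS. None of these isolates physical function or quality of life, so this does not answer the point.

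**Conclusion.** The point holds as a gap between a stated comparative objective and the planned analysis. HAQ-DI, SF-36v2 PCS and MCS, ACR 50 and ACR 70 move from a protocol-planned ANCOVA or CMH comparison to per-arm description, while two exploratory indices gain a comparison. No reason in Section 11 accounts for this. sPGA, BSA, the ACR components, and ACR 20 and MDA at other visits are affected in the same way.

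The consequence is limited. The primary and key secondary tests, the gatekeeping chain and the family-wise error rate of 0.05 do not change. The conclusion rests on comparing the endpoint lists and method sections, not on a numerical assumption. The precision figures assume 252 to 280 evaluable subjects per arm, and the ACR 50/70 power range also assumes the response rates stated with it.

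**What to change.** Add the following to the list in SAP 10.5.2 and to item 3 of SAP Section 11, each etanercept arm versus methotrexate at week 24:

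- change in HAQ-DI, SF-36v2 PCS and SF-36v2 MCS, by the ANCOVA already in 10.5.2;
- ACR 50 and ACR 70, by the same stratified CMH test.

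Report an adjusted mean difference or a stratified risk difference with a 95% confidence interval on the original scale, and mark p-values descriptive. If the data are non-normal, use the van der Waerden rank ANCOVA for the p-value only, because its treatment difference is not in HAQ-DI or SF-36 units. For secondary endpoints that stay descriptive, such as sPGA, BSA and the ACR components, state the reason in Section 11.

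The cost is SAP wording, 10 more nominal comparisons without multiplicity adjustment, and some programming, since 10.5.2 does not now specify intervals. No confirmatory alpha is used and no new data are needed.
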